Appendix 8: Study Details Specific to Atezo + CAPOX + Tira Arm (cont.)

Patients who require corticosteroid therapy for more than 7 days after completion of radiotherapy must be discontinued from study treatment.

- Anti-convulsant therapy, if required, is administered at a stable dose.

Premedication with antihistamines, antipyretic medications, and/or analgesics may be administered for the second and subsequent atezolizumab and tiragolumab infusions only, at the discretion of the investigator.

In general, investigators should manage a patient's care (including preexisting conditions) with supportive therapies other than those defined as cautionary or prohibited therapies as clinically indicated, per local standard practice. Patients who experience infusion-associated symptoms may be treated symptomatically with acetaminophen, ibuprofen, diphenhydramine, and/or H₂-receptor antagonists (e.g., famotidine, cimetidine), or equivalent medications per local standard practice. Serious infusion-associated events manifested by dyspnea, hypotension, wheezing, bronchospasm, tachycardia, reduced oxygen saturation, or respiratory distress should be managed with supportive therapies as clinically indicated (e.g., supplemental oxygen and β_2 -adrenergic agonists; see [Appendix 4](#)).

A8–4.2.2 Cautionary Therapy for Atezo + CAPOX + Tira Arm

A8–4.2.2.1 Corticosteroids, Immunosuppressive Medications, and Tumor Necrosis Factor– α Inhibitors

Systemic corticosteroids, immunosuppressive medications, and tumor necrosis factor– α (TNF- α) inhibitors may attenuate potential beneficial immunologic effects of treatment with atezolizumab and/or tiragolumab. Therefore, in situations in which systemic corticosteroids, immunosuppressive medications, or TNF- α inhibitors would be routinely administered, alternatives, including antihistamines, should be considered. If the alternatives are not feasible, systemic corticosteroids, immunosuppressive medications, and TNF- α inhibitors may be administered at the discretion of the investigator.

Systemic corticosteroids or immunosuppressive medications are recommended, at the discretion of the investigator, for the treatment of specific adverse events when associated with atezolizumab and/or tiragolumab therapy (refer to [Appendix 5](#) for details).

A8–4.2.2.2 Herbal Therapies

Concomitant use of herbal therapies is not recommended because their pharmacokinetics, safety profiles, and potential drug-drug interactions are generally unknown. However, herbal therapies not intended for the treatment of cancer (see Section [A8–4.2.3](#)) may be used during the study at the discretion of the investigator.

A8–4.2.2.3 Medications Given with Precaution Concomitantly with CAPOX

The following medications should be used with precaution during treatment with CAPOX:

- Anticoagulants: Patients who receive concomitant capecitabine and oral coumadin-derivative anticoagulant therapy such as warfarin should have their anticoagulant response (INR or prothrombin time) monitored frequently in order to adjust the anticoagulant dose.
- Phenytoin: Monitor phenytoin levels in patients taking capecitabine concomitantly with phenytoin. The phenytoin dose may need to be reduced.
- Leucovorin: The concentration 5-FU is increased and its toxicity may be enhanced by leucovorin.
- CYP2C9 substrates: Patients who are treated with capecitabine and other sensitive CYP2C9 substrate or a CYP2C9 substrate with narrow therapeutic index should be closely monitored for toxicity.
- Because platinum-containing species are eliminated primarily through the kidneys, clearance of these products may be decreased by co-administration of potentially nephrotoxic compounds. Co-administration of oxaliplatin with medicinal products known to cause nephrotoxicity is not recommended.

A8–4.2.3 Prohibited Therapy for Atezo + CAPOX + Tira Arm

Use of the following concomitant therapies is prohibited as described below:

- Concomitant therapy intended for the treatment of cancer (including, but not limited to, chemotherapy, hormonal therapy, immunotherapy, radiotherapy, and herbal therapy), whether health authority–approved or experimental, for various time periods prior to starting study treatment, depending on the agent (see Section 4.1.2), and during study treatment until disease progression is documented and the patient has discontinued study treatment, with the exception of palliative radiotherapy and radiotherapy to the brain under circumstances outlined in Section A8–4.2.1
- Concomitant use of herbal therapies and traditional Chinese medicine with anti-cancer activity included in the label
- Investigational therapy within 28 days prior to initiation of study treatment and during study treatment
- Use of allopurinol during treatment with capecitabine
- Live, attenuated vaccines (e.g., FluMist®) within 4 weeks prior to initiation of study treatment, during treatment with atezolizumab and/or tiragolumab, and for 5 months after the final dose of atezolizumab or 90 days after the final dose of tiragolumab, whichever is later

Appendix 8: Study Details Specific to Atezo + CAPOX + Tira Arm (cont.)

- Systemic immunostimulatory agents (including, but not limited to, interferons and interleukin-2) within 4 weeks or 5 drug-elimination half-lives (whichever is longer) prior to initiation of study treatment and during study treatment because such agents could potentially increase the risk for autoimmune conditions when given in combination with atezolizumab and/or tiragolumab

A8–4.3 CONTRACEPTION REQUIREMENTS FOR ATEZO + CAPOX + TIRA ARM

Contraception requirements for women and men in the Atezo + CAPOX + Tira arm are outlined below:

- For women of childbearing potential: agreement to remain abstinent (refrain from heterosexual intercourse) or use contraception, as defined below:

Women must remain abstinent or use contraceptive methods with a failure rate of < 1% per year during the treatment period and for 90 days after the final dose of tiragolumab, 5 months after the final dose of atezolizumab, 6 months after the final dose of capecitabine, and 9 months after the final dose of oxaliplatin.

A woman is considered to be of childbearing potential if she is postmenarchal, has not reached a postmenopausal state (≥ 12 continuous months of amenorrhea with no identified cause other than menopause), and is not permanently infertile due to surgery (i.e., removal of ovaries, fallopian tubes, and/or uterus) or another cause as determined by the investigator (e.g., Müllerian agenesis). The definition of childbearing potential may be adapted for alignment with local guidelines or regulations.

Examples of contraceptive methods with a failure rate of < 1% per year include bilateral tubal ligation, male sterilization, hormonal contraceptives that inhibit ovulation, hormone-releasing intrauterine devices, and copper intrauterine devices.

The reliability of sexual abstinence should be evaluated in relation to the duration of the clinical trial and the preferred and usual lifestyle of the patient. Periodic abstinence (e.g., calendar, ovulation, symptothermal, or postovulation methods) and withdrawal are not adequate methods of contraception. If required per local guidelines or regulations, locally recognized adequate methods of contraception and information about the reliability of abstinence will be described in the local Informed Consent Form.
- For men: agreement to remain abstinent (refrain from heterosexual intercourse) or use a condom, and agreement to refrain from donating sperm, as defined below:

With a female partner of childbearing potential or pregnant female partner, men must remain abstinent or use a condom during the treatment period and for 3 months after final dose of capecitabine, 6 months after final dose of oxaliplatin, and for 90 days after the final dose of tiragolumab to avoid exposing the embryo. Men must refrain from donating sperm during this same period.

Appendix 8: Study Details Specific to Atezo + CAPOX + Tira Arm (cont.)

The reliability of sexual abstinence should be evaluated in relation to the duration of the clinical trial and the preferred and usual lifestyle of the patient. Periodic abstinence (e.g., calendar, ovulation, symptothermal, or postovulation methods) and withdrawal are not adequate methods of preventing drug exposure. If required per local guidelines or regulations, information about the reliability of abstinence will be described in the local Informed Consent Form.

Male patients should be advised regarding the conservation of sperm prior to treatment because of the possibility of irreversible infertility resulting from therapy with capecitabine and oxaliplatin.

A8–5 ASSESSMENT OF SAFETY FOR ATEZO + CAPOX + TIRA ARM

A8–5.1 SAFETY PLAN FOR ATEZO + CAPOX + TIRA ARM

The safety plan for patients in this study is based on clinical experience with atezolizumab, CAPOX, and tiragolumab in completed and ongoing studies. The anticipated important safety risks are outlined below (see Sections [A8–5.1.1](#), [A8–5.1.2](#), [A8–5.1.3](#), and [A8–5.1.4](#)). Guidelines for management of patients who experience specific adverse events are provided in Section [A8–5.1.5](#).

Measures will be taken to ensure the safety of patients participating in this study, including the use of stringent inclusion and exclusion criteria and close monitoring of patients during the study.

Administration of study treatment will be performed in a monitored setting in which there is immediate access to trained personnel and adequate equipment and medicine to manage potentially serious reactions. Adverse events will be reported as described in Sections [5.4–5.6](#).

A8–5.1.1 Risks Associated with Atezolizumab

Atezolizumab has been associated with risks such as the following: IRRs and immune-mediated hepatitis, pneumonitis, colitis, pancreatitis, diabetes mellitus, hypothyroidism, hyperthyroidism, adrenal insufficiency, hypophysitis, Guillain-Barré syndrome, myasthenic syndrome or myasthenia gravis, facial paresis, myelitis, meningoencephalitis, myocarditis, pericardial disorders, nephritis, myositis, and severe cutaneous adverse reactions. In addition, immune-mediated reactions may involve any organ system and lead to hemophagocytic lymphohistiocytosis (HLH). See [Appendix 5](#) of the protocol and Section 6 of the Atezolizumab Investigator's Brochure for a detailed description of anticipated safety risks for atezolizumab.

A8–5.1.2 Risks Associated with CAPOX

In prior clinical trials of capecitabine, the following safety signals were identified: diarrhea, nausea, vomiting, stomatitis, cardiotoxicity, hepatotoxicity, hand–foot

Appendix 8: Study Details Specific to Atezo + CAPOX + Tira Arm (cont.)

syndrome, and hematologic toxicity. Patients should be advised to avoid prolonged exposure to sunlight because of the risk of photosensitivity with capecitabine.

In prior clinical trials of oxaliplatin, the following safety signals were identified: sensory and/or motor neuropathy, allergic reactions, pharyngolaryngeal dysesthesia, interstitial lung disease and pulmonary fibrosis, hepatotoxicity, and hematologic toxicity.

For more details regarding the safety profile of capecitabine and oxaliplatin, see the respective local prescribing information.

A8–5.1.3 Risks Associated with Tiragolumab

[REDACTED]

[REDACTED] While clinical evaluation of tiragolumab is limited and not all risks are known, as an antagonist of TIGIT, tiragolumab is anticipated to enhance T-cell and NK-cell proliferation, survival, and function. Therefore, tiragolumab may increase the risk of autoimmune inflammation (also described as [REDACTED])

A8–5.1.3.1 Infusion-Related Reactions

[REDACTED]

[REDACTED] Clinical signs and symptoms of such reactions may include rigors, chills, wheezing, pruritus, flushing, rash, hypotension, hypoxemia, and fever. [REDACTED]

[REDACTED] The majority of events were mild to moderate and manageable.

To minimize the risk and sequelae of IRRs, [REDACTED]

[REDACTED]

Subsequent infusions and observation times may be shortened if the preceding infusion was well tolerated. All infusions of tiragolumab will be administered in an appropriate medical setting.

See Section [A8–4.1.2.3](#) detailed guidance on administration of tiragolumab in this study. See [Appendix 4](#) for guidance on anaphylaxis precautions and [Appendix 5](#) for guidance on the management of IRRs.

Appendix 8: Study Details Specific to Atezo + CAPOX + Tira Arm (cont.)

[REDACTED]

[REDACTED]

[REDACTED]

[REDACTED]

[REDACTED]

[REDACTED]

[REDACTED]

[REDACTED]

A8–5.1.3.5 Embryofetal Toxicity

[REDACTED]

[REDACTED]

[REDACTED] No reproductive or teratogenicity

studies in animals have been conducted with tiragolumab. There are no clinical studies of tiragolumab in pregnant women. Tiragolumab should not be administered to pregnant women.

Refer to Section 6 of the Tiragolumab Investigator's Brochure for a detailed description of embryofetal toxicity.

A8–5.1.4 Risks Associated with Combination Use of Atezolizumab, CAPOX, and Tiragolumab

The following adverse events are potential overlapping toxicities associated with combination use of atezolizumab with tiragolumab and CAPOX: [REDACTED]

[REDACTED]

Neutropenia and [REDACTED] associated with chemotherapy may aggravate the known adverse reaction of [REDACTED] for tiragolumab in combination with atezolizumab, and increase the risk for developing infection in patients receiving atezolizumab and tiragolumab in combination with chemotherapy.

Given the mechanism of action for atezolizumab and tiragolumab, [REDACTED] [REDACTED] are potential overlapping toxicities associated with combination use of these two agents.

A8–5.1.5 Management of Patients Who Experience Specific Adverse Events in Atezo + CAPOX + Tira Arm

A8–5.1.5.1 Dose Modifications Atezolizumab and Tiragolumab

There will be no dose modifications for atezolizumab and tiragolumab in this study.

Capecitabine

The capecitabine dose can be modified as presented in [Table 4](#) for the management of drug-related toxicities. Once the dose has been reduced, it cannot be increased later. Omitted doses of capecitabine because of toxicity will not be replaced.

Table 4 Dose Modifications for Capecitabine Drug-Related Toxicities

Toxicity ^a	Action to Be Taken for Current Treatment	Dose Modification for the Next Treatment (% of Starting Dose)
Grade 1	Maintain dose level.	Maintain dose level.
Grade 2		
First occurrence	Withhold until resolved to Grade 1 or better.	100% (1000 mg/m ²)
Second occurrence		75% (750 mg/m ²)
Third occurrence		50% (500 mg/m ²)
Fourth occurrence	Discontinue permanently.	—
Grade 3		
First occurrence	Withhold until resolved to Grade 1 or better.	75% (750 mg/m ²)
Second occurrence		50% (500 mg/m ²)
Third occurrence	Discontinue permanently.	—
Grade 4		
First occurrence	Discontinue permanently or continue at the discretion of the investigator until resolved to Grade 1 or better.	50% (500 mg/m ²)

^a Graded according to the National Cancer Institute Common Terminology Criteria for Adverse Events, Version 5.0.

Oxaliplatin

Dose Modifications for Patients with Neurotoxicity

The following dose modifications will be made for patients with neurotoxicity:

- For Grade 2 peripheral sensory neuropathy (moderate paresthesia or dysesthesia), or limiting instrumental activities of daily living, omit oxaliplatin. When toxicity resolves to Grade 1 or better, resume oxaliplatin to 75% of the initial dose. If oxaliplatin is omitted for 6 weeks (two consecutive cycles) for neurologic toxicity, discontinue oxaliplatin.
- For Grade 3 and 4 peripheral sensory neuropathy (severe paresthesia or dysesthesia) or limiting self-care activities of daily living, discontinue oxaliplatin.

Dose Modifications for Patients with Renal Impairment

The following dose modifications will be made for patients with renal impairment:

- For normal renal function or mild to moderate renal impairment (creatinine clearance > 50 mL/min), the full dose of oxaliplatin can be administered.
- For severe renal impairment, the oxaliplatin dose should be reduced to 75% of the initial dose.

[figure not shown]

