Control Method:	Active comparator	Population Diagnosis or Condition:	Inoperable locally advanced, metastatic, or advanced GC or GEJC
Interventional Model:	Parallel group	Population Age:	Age \geq 18 years
Test Compounds:	Atezolizumab, tiragolumab	Site Distribution:	Multi-site
Active Comparator:	Atezolizumab in combination with capecitabine plus oxaliplatin	Study Intervention Assignment Method:	Randomization
Number of Arms:	2	Number of Participants to Be Enrolled:	Approximately 40–90 patients

GC = gastric carcinoma; GEJC = gastroesophageal junction carcinoma.

STUDY TREATMENT

The study treatment is summarized in Table 3.

Table 3 Study Treatment

Stage 1 Study Treatments	
Treatment Group	Dose, Route, and Regimen (drugs listed in order of administration)
Atezo + CAPOX (control group treatment combination) (21-day cycles)	
 • Atezolizumab 1200 mg by IV infusion on Day 1 • Capecitabine 1000 mg/m² orally twice daily on Days 1–14 ^a • Oxaliplatin 130 mg/m² by IV infusion on Day 1 ^a
Atezo + CAPOX + Tira (treatment combination) (21-day cycles)	
 • Atezolizumab 1200 mg by IV infusion on Day 1 • Tiragolumab 600 mg by IV infusion on Day 1 • Capecitabine 1000 mg/m² orally twice a day on Days 1–14 ^a • Oxaliplatin 130 mg/m² by IV infusion on Day 1 ^a

Atezo = atezolizumab; CAPOX = capecitabine plus oxaliplatin; Tira = tiragolumab.

^a Treatment for up to six cycles.

There will be no dose modifications for atezolizumab *or* tiragolumab in this study.

Capecitabine Dose Modification

The capecitabine dose can be modified as presented in Table 4 for the management of drug-related toxicities. Once the dose has been reduced, it cannot be increased later. Omitted doses of capecitabine because of toxicity will not be replaced.

Table 4 Dose Modification for Capecitabine for Drug-Related Toxicities

Toxicity ^a	Action to Be Taken for Current Treatment	Dose Modification for the Next Treatment (% of Starting Dose)
Grade 1	Maintain dose level.	Maintain dose level.
Grade 2		
First occurrence	Withhold until resolved to Grade 1 or better.	100% (1000 mg/m ²)
Second occurrence		75% (750 mg/m ²)
Third occurrence		50% (500 mg/m ²)
Fourth occurrence	Discontinue permanently.	—
Grade 3		
First occurrence	Withhold until resolved to Grade 1 or better.	75% (750 mg/m ²)
Second occurrence		50% (500 mg/m ²)
Third occurrence	Discontinue permanently.	—
Grade 4		

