First occurrence	Discontinue permanently or continue at the discretion of the investigator once the event has resolved to Grade 1 or better.	50% (500 mg/m ²)

^a Graded according to the National Cancer Institute Common Terminology Criteria for Adverse Events, Version 5.0.

Oxaliplatin Dose Modification

Dose Modifications for Patients with Neurotoxicity

- For Grade 2 peripheral sensory neuropathy (moderate paresthesia or dysesthesia) or limiting instrumental activities of daily living, omit oxaliplatin. When toxicity resolves to Grade 1 or better, resume oxaliplatin to 75% of the initial dose. If oxaliplatin is omitted for 6 weeks (two consecutive cycles) for neurologic toxicity, discontinue oxaliplatin.
- For Grade 3 and 4 peripheral sensory neuropathy (severe paresthesia or dysesthesia) or limiting self-care activities of daily living, discontinue oxaliplatin.

Dose Modifications for Patients with Renal Impairment

- For normal renal function or mild to moderate renal impairment (creatinine clearance > 50 mL/min), the full dose of oxaliplatin can be administered.
- For severe renal impairment, the oxaliplatin dose should be reduced to 75% of the initial dose.

Dose Modifications for Patients with Hematologic Toxicity

- For Grade 2 and 3 thrombocytopenia, the oxaliplatin dose should be reduced to 75% of the initial dose. For Grade 4 thrombocytopenia, the dose should be reduced to 50% of the initial dose.
- For Grade 3 and 4 neutropenia or febrile neutropenia, the oxaliplatin dose should be reduced to 75% of the initial dose.

DURATION OF PARTICIPATION

Treatment will continue until disease progression per Response Evaluation Criteria in Solid Tumors, Version 1.1. The total length of the study, from screening of the first patient to the end of the study, is expected to be approximately 3–5 years.

COMMITTEES

Independent Committees:	Not applicable
Other Committees:	Internal Monitoring Committee

LIST OF ABBREVIATIONS AND DEFINITIONS OF TERMS

Abbreviation	Definition
5-FU	5-fluorouracil
ADA	anti-drug antibody
ASTCT	American Society for Transplantation and Cellular Therapy
Atezo	atezolizumab
Atezo + CAPOX	atezolizumab in combination with capecitabine and oxaliplatin
Atezo + CAPOX + Tira	atezolizumab in combination with capecitabine, oxaliplatin, and tiragolumab
CAPOX	capecitabine in combination with oxaliplatin
CIT	cancer immunotherapy
COVID-19	coronavirus disease 2019
CPS	combined positive score
CRS	cytokine release syndrome
CT	computed tomography

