4.5 STUDY ASSESSMENTS

A schedule of activities to be performed during the study is provided for each treatment arm (see [Appendix 7](#) and [Appendix 8](#)). All activities must be performed and documented for each patient. Patients will be closely monitored for safety and tolerability throughout the study. Patients should be assessed for toxicity prior to each dose; dosing will occur only if the clinical assessment and local laboratory test values are acceptable.

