Appendix 8: Study Details Specific to Atezo + CAPOX + Tira Arm (cont.)

CAPOX will continue for up to six cycles and patients will be offered continued treatment with atezolizumab as long as they are experiencing clinical benefit in the opinion of the investigator. If oxaliplatin treatment is discontinued during the first six cycles, patients are encouraged to continue chemotherapy with capecitabine, atezolizumab, and tiragolumab as long as they are experiencing clinical benefit in the opinion of the investigator. The Medical Monitor is available to advise as needed. If capecitabine treatment is discontinued during the first six cycles, patients are encouraged to continue chemotherapy with oxaliplatin, atezolizumab, and tiragolumab as long as they are experiencing clinical benefit in the opinion of the investigator, the Medical Monitor is available to advise as needed.

A8–5.1.5.3 Management Guidelines for Adverse Events

[Appendix 5](#) provides guidelines for the management of patients who experience atezolizumab- and/or tiragolumab-associated adverse events. It is recommended that atezolizumab and/or tiragolumab be withheld or discontinued per the guidelines provided in [Appendix 5](#).

For cases in which management guidelines are not covered in [Appendix 5](#), patients should be managed and treatments should be withheld or discontinued as deemed appropriate by the investigator according to best medical judgment.

Guidelines for management of patients who experience specific adverse events related to CAPOX regimen are provided in Section [A8–5.1.5.1](#). The treating physician may use discretion in modifying the dose modification guidelines, depending on the severity of toxicity and an assessment of the benefit versus risk for the patient, with the goal of maximizing patient compliance and access to supportive care.

Chemotherapy should be discontinued if ANC and platelets do not recover to $\geq 1000/\mu\text{L}$ and $\geq 75,000/\mu\text{L}$, respectively, after treatment is delayed by 3 weeks.

[REDACTED]

[REDACTED]

- [REDACTED]

- [illegible]

A8-5.3.1 Pregnancies in Female Patients

GC and GEJC Combinations—F. Hoffmann-La Roche Ltd
194/Protocol YO43408, Version 5

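### The experimental-arm dosing table, read literally, lets capecitabine continue through an unresolved Grade 4 toxicity, contrary to the Synopsis and the control-arm table

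*Combined protocol and SAP*

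**What the plan says.** The capecitabine dose-modification rules appear three times: Synopsis Table 4, Table 3 in A7-5.1.4.1 (control arm) and Table 4 in A8-5.1.5.1 (experimental arm). The disputed text is the action for current treatment at a first Grade 4 event.

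- **Experimental arm (A8 Table 4):** "Discontinue permanently or continue at the discretion of the investigator until resolved to Grade 1 or better".
- **Synopsis Table 4 and control arm (A7 Table 3), in identical words:** "Discontinue permanently or continue at the discretion of the investigator once the event has resolved to Grade 1 or better".

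The Synopsis introduces its table without restricting it to an arm: "The capecitabine dose can be modified as presented in Table 4 for the management of drug-related toxicities". The sentence just before that section rules out dose changes for atezolizumab and for tiragolumab, and the Synopsis treatment table lists both regimens. The Synopsis rule therefore applies to the experimental arm too.

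For capecitabine-related events in the experimental arm, A8-5.1.5.3 directs the investigator to A8-5.1.5.1: "Guidelines for management of patients who experience specific adverse events related to CAPOX regimen are provided in Section" A8-5.1.5.1.

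**The concern.** *Once* makes recovery a precondition for further dosing. *Until* permits dosing up to the moment of recovery. A reader who takes the Appendix 8 row at its word may keep a patient on capecitabine during a Grade 4 event. The experimental arm then has two incompatible instructions, one in the Synopsis and one in its own appendix. It also has a looser rule than the control arm, with no reason given.

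What is at stake is patient safety. Capecitabine is taken by mouth twice daily on Days 1–14, while the treatment visits in the A8-6 schedule fall on Day 1 of each cycle. An event in mid-cycle is when a site has to decide whether the patient goes on taking tablets, and this row is meant to answer that question. A8-5.1.4 also warns that chemotherapy-associated neutropenia may raise the risk of infection when atezolizumab and tiragolumab are given with chemotherapy.

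**Working it through.** The plan has no figure to reproduce here. The check is a comparison of text, followed by a simple count of how many patients the row could reach.

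**1. The Grade 4 row in the three tables**

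| Element | Synopsis Table 4 | A7 Table 3 (control) | A8 Table 4 (experimental) |
|---|---|---|---|
| Option 1 | Permanent discontinuation | Same | Same |
| Option 2 | Continue at discretion, *once* resolved | Continue at discretion, *once* resolved | Continue at discretion, *until* resolved |
| Recovery threshold | Grade 1 or better | Same | Same |
| Next dose | 50% (500 mg/m²) | Same | Same |

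Only the timing phrase in option 2 differs, and only in one table of three. The Grade 1, 2 and 3 rows agree in all three.

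**2. The row against its own section.** In A8 Table 4, Grade 2 and Grade 3 events short of the final listed occurrence carry the instruction "Withhold until resolved to Grade 1 or better". For Grade 2 neuropathy the same section omits oxaliplatin and then says "When toxicity resolves to Grade 1 or better, resume oxaliplatin to 75% of the initial dose". Read literally, the Grade 4 row would be more permissive than the Grade 2 row. That ordering makes no clinical sense, so the wording is probably a slip, perhaps carried down from the rows above. That explanation is an inference.

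**3. Whether it could be an artefact.** The A8 sentence is complete and grammatical, contains no redaction, and stands in the current text rather than in the amendment summary.

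**4. Patients covered.** Section 3.1.2 and its Table 4 plan 20 experimental patients in the preliminary phase and 25 more on expansion: 20 + 25 = 45. Capecitabine runs for up to six cycles.

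**5. Reach of the row.** The documents give no Grade 4 rate for capecitabine. Section 1.3 cites Grade 3 and 4 toxicity in up to 77% of patients on platinum doublets, but this separates out neither Grade 4 nor capecitabine. Assume that a proportion p of patients, from 1% to 10%, has a Grade 4 capecitabine-related event. The expected number for whom the row is consulted is n × p:

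| n | p = 1% | p = 5% | p = 10% |
|---|---|---|---|
| 20 | 0.2 | 1.0 | 2.0 |
| 45 | 0.45 | 2.25 | 4.5 |

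These figures count consultations of the row, not harm. For harm to follow, the investigator must also choose not to discontinue and must read the row literally.

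**The case against.** The strongest reply is that no trained oncology investigator would read the row as permission to dose through a Grade 4 event. The rows directly above say to withhold, the Synopsis states the intended rule, and the branch is discretionary in all three tables. A8-5.1.5.3 treats the tables as guidelines: "The treating physician may use discretion in modifying the dose modification guidelines". On this view the point is editorial.

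Other text also points towards interruption:

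- A8-5.1.5.2 allows CAPOX to be suspended for treatment-related toxicity. After more than 21 days of withholding for toxicity, CAPOX should stop unless benefit is likely.
- A8-5.1.5.3 stops chemotherapy if neutrophils and platelets have not recovered after a three-week delay, which presupposes that treatment was held.
- Section 4.5 asks for toxicity assessment before each dose: "dosing will occur only if the clinical assessment and local laboratory test values are acceptable".
- Section 4.6.1 requires discontinuation for intolerable toxicity or a condition that jeopardizes safety.
- Sections 5.2.2 and 5.4 require life-threatening events to be reported within 24 hours, and Section 5.4.1 gives round-the-clock access to a Medical Monitor.

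Much of this stands. It makes harm unlikely and shows what was intended. It does not make the row correct. The suspension and discretion clauses are permissive, and discretion works from a stated default that is wrong here. Reporting and medical advice set no dosing rule, and the general requirements in Sections 4.5 and 4.6.1 rest on judgement at the site. The Synopsis does give the right rule, but nothing in Appendix 8 says that it prevails, and a site should not have to reconcile two sections during a Grade 4 event. The reach figures rest on an assumed rate and should not decide how much weight the point gets.

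**Conclusion.** The concern holds. As written, the Grade 4 row of A8 Table 4 contradicts Synopsis Table 4 for the same patients, differs without explanation from the control-arm table, and is out of order with the lower-grade rows of its own table. The error is confined to the timing phrase of one optional branch. It is probably a drafting slip, and the intended meaning can be recovered from the Synopsis.

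It should be fixed because it is a dosing instruction for a life-threatening grade of toxicity in the experimental arm. Its practical reach is small under the assumed 1% to 10% rate, and actual harm would be rarer still. Sample size, endpoints and analysis are not affected.

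**What to change.** In A8-5.1.5.1, Table 4, replace the Grade 4 action with the text already used in Synopsis Table 4 and A7 Table 3: "Discontinue permanently or continue at the discretion of the investigator once the event has resolved to Grade 1 or better". Leave the 50% next dose as it is. Tell sites about the correction when it is made, so that nobody works from the old row.

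The cost is one line in the next amendment and a site notice.
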